## 2. Protocol Synopsis

Postmarket Solyx™ Study PS120093: A Prospective, Non-Randomized, Parallel Cohort, Multi-center Study of the Solyx™ Single Incision Sling System vs. the Obtryx™ II Sling System for the Treatment of Women with Stress Urinary Incontinence	
Objective(s)	The purpose of this study is to compare a single incision midurethral sling to a standard outside-in transobturator sling for the treatment of female stress urinary incontinence. It is hypothesized that the single incision sling will be non-inferior to the transobturator device in safety and effectiveness.
Test Device	Solyx™ Single Incision Sling System
Control Device	Standard outside-in transobturator sling (i.e. Obtryx™ II Sling System)
Study Design	
Prospective, non-randomized, parallel cohort, multi-center study
 
All study procedures will be standardized for uniformity. Physicians will have to document a minimum of ~10 procedures per device prior to participation in order to document competency and experience. Surgeons in the Obtryx cohort must complete a minimum of 5 Obtryx II cases to meet their case prerequisite obligation. [REDACTED]
 
Concomitant procedures including pelvic floor repair can occur, per physician discretion. All concomitant procedures performed will be recorded.
 
Subjects who undergo a medical intervention (surgical or non-surgical) to treat recurrence, persistence of SUI, or a mesh complication will be followed to 36 months from the initial study procedure.

Planned Number of Subjects	Assuming 20% lost to follow-up at 36 months, approximately 280 subjects (140 in each study arm) are planned
Planned Number of Centers / Countries	Up to 30 study centers

**Postmarket Solyx™ Study PS120093: A Prospective, Non-Randomized, Parallel Cohort, Multi-center Study of the Solyx™ Single Incision Sling System vs. the Obtryx™ II Sling System for the Treatment of Women with Stress Urinary Incontinence**

Primary Endpoint	The primary endpoint is an assessment of improvement in stress urinary incontinence at 36 months as compared to Baseline, by a composite of objective and subjective measures: negative cough stress test with protocol required bladder fill procedure and a subject self-reported improvement in their condition, through the Patient Global Impression of Improvement (PGI-I).
[REDACTED]	[REDACTED]
Method of Assigning Subjects to Treatment	This study is a non-randomized, parallel cohort study. Physicians and study centers will be selected based on their device experience and will be device-specific centers (i.e. Solyx™ or Obtryx II™ subjects only). Approximately 140 subjects will be enrolled in each respective cohort.
Follow-up Schedule	Study follow-up duration is for 3 years from primary study procedure: 
 
• Screening/Enrollment Visit
 
• Pre-operative/Baseline Visit
 
• Surgery and Discharge
 

Postmarket Solyx™ Study PS120093: A Prospective, Non-Randomized, Parallel Cohort, Multi-center Study of the Solyx™ Single Incision Sling System vs. the Obtryx™ II Sling System for the Treatment of Women with Stress Urinary Incontinence
	
	
 
• Week 2 Visit
 
• Week 6 Visit
 
• Month 6 Visit
 
• Month 12 Visit
 
• Month 18 Visit
 
• Month 24 Visit
 
• Month 36 Visit (End of study)
 

Study Duration
	
Approximately 3 years from last subject enrolled

Key Inclusion Criteria
	
 
1. Female ≥ 18 years of age
 
2. Willing and able to comply with the study procedures and provide written informed consent to participate in the study (subject or legal representative)
 
3. Diagnosed with predominant SUI confirmed by positive cough stress test during the protocol required bladder fill procedure (see manual of operations)
 
4. Confirmed SUI is greater than urge incontinence with MESA
 
5. Cystometric capacity ≥ 300 cc
 
6. Post-void residual (PVR) of ≤ 150 cc
 
7. Medically approved for general, regional or monitored anesthesia
 

**Postmarket Solyx™ Study PS120093: A Prospective, Non-Randomized, Parallel Cohort, Multi-center Study of the Solyx™ Single Incision Sling System vs. the Obtryx™ II Sling System for the Treatment of Women with Stress Urinary Incontinence**


Key Exclusion Criteria
	
 
1. Subjects who are pregnant, lactating, or planning future pregnancies
 
2. Subjects with a chief complaint of overactive bladder
 
3. Subjects with a pattern of recurrent urinary tract infections, defined as <math>\geq 2</math> culture-proven urinary tract infections during a 6-month period prior to surgery or <math>\geq 3</math> in a 12-month period
 
4. Subjects with previous surgical procedures for SUI including bulking, urethral sling, bone anchor, Burch procedure, pubo-vaginal sling, and MMK procedure. Previous surgical procedures for SUI does not include Kelly plication, Botox, anterior repair, or Inter-Stim.
 
5. Subjects with prior pelvic organ prolapse surgery who experienced mesh complications
 
6. Subjects with previous radiation therapy to the pelvis
 
7. Subjects with known or suspected hypersensitivity to polypropylene mesh
 
8. Subjects with any of the following confounding conditions:             
 
a. Neurogenic bladder
 
b. Urethral stricture and bladder neck contracture
 
c. Bladder stones or tumors
 
d. Urinary tract fistula or diverticula
 
e. Pathology which would compromise implant placement including subjects currently taking anticoagulation therapy
 
f. Pathology that would limit blood supply or infections that would compromise healing including chemotherapy, systemic steroids and systemic immunosuppressants
 
 
 
9. Subjects with diabetes and an A1c <math>\geq 7\%</math>
 
10. Non-English speaking subjects
 
11. Subjects who have participated in an investigational study (medical device or drug) within 30 days of study entry that may impact analysis of this device or have previously participated in the current study
 

--------------------------------------	---

**Postmarket Solyx™ Study PS120093: A Prospective, Non-Randomized, Parallel Cohort, Multi-center Study of the Solyx™ Single Incision Sling System vs. the Obtryx™ II Sling System for the Treatment of Women with Stress Urinary Incontinence**

**Primary Statistical Hypothesis**

The single incision sling will be non-inferior to the standard outside-in transobturator sling for the treatment of female stress urinary incontinence in safety and effectiveness at 36 months as compared to Baseline.

Statistical testing will be performed to determine if success rate of improvement in stress urinary incontinence at 36 months of single incision sling (treatment) group will be non-inferior to transobturator device (control) group. The null hypothesis is that the success rate in treatment group is less than or equal to the success rate in control group minus margin:

$$H_0: \pi_{treatment} - \pi_{control} \leq -\Delta$$

The alternative hypothesis is:

$$H_a: \pi_{treatment} - \pi_{control} > -\Delta$$

where  $\pi_{treatment}$  and  $\pi_{control}$  are the success rate of improvement in stress urinary incontinence at 36 months in treatment group and control group respectively, and  $\Delta$  is defined as the non-inferiority margin.

**Postmarket Solyx™ Study PS120093: A Prospective, Non-Randomized, Parallel Cohort, Multi-center Study of the Solyx™ Single Incision Sling System vs. the Obtryx™ II Sling System for the Treatment of Women with Stress Urinary Incontinence**

Statistical Test Method	For each of the primary endpoint and serious adverse events, non-inferiority of the single-incision sling will be evaluated using a two-sided 90% confidence interval for the treatment difference (single-incision minus transobturator). The confidence interval will be calculated based on the pooling of treatment differences across propensity score strata. All statistical analyses will be performed by the Sponsor per the Statistical Analysis Plan. [REDACTED]
--------------------------------	---

[REDACTED]	[REDACTED]
------------	------------

#### 4. Introduction

The prevalence of urinary incontinence in adult women is estimated at 4%-35%. It is considered severe in about 3%-17% of adult women. Urinary incontinence is considered a “potentially debilitating social problem which leads to high health care costs.” The most common surgery for stress urinary incontinence (SUI) is the minimally invasive sling surgery which has replaced the Burch colposuspension as gold standard treatment for female urinary stress incontinence. Incontinence surgery has become a routine part of urologic care but often can be difficult to manage complications and recurrent incontinence.

Mid-urethral slings have been reported in published literature to be highly efficacious in managing SUI in women. The transobturator placement was developed to decrease morbidity, but has been noted to be associated with a higher incidence of thigh pain than the retropubic approach. Single incision slings were developed to offer the benefits of the transobturator approach in addition to a minimally invasive approach through a single 1.5 cm incision to the vagina and without exiting the skin.

### 5. Device Description

The Solyx™ SIS (Single Incision Sling) System is a sterile single use system consisting of one (1) delivery device and one (1) mesh assembly. The mesh assembly is comprised of a polypropylene knitted mesh with polypropylene carriers at each end of the distal mesh. The carrier is designed to be placed on the tip of the delivery device. The disposable delivery device consists of a handle, a [REDACTED] shaft and a deployment mechanism. The delivery device is designed to facilitate the passage of the mesh assembly through bodily tissues for placement into the obturator internus muscle.

The Obtryx™ II System is a sterile, single use system consisting of two (2) delivery devices and one (1) mesh assembly. The mesh assembly is comprised of a polypropylene knitted mesh with dilator legs and a center tab. At the distal ends of the dilator legs there are association loops designed to be placed in the needle slot of the distal end of the delivery device. The disposable delivery device consists of a handle with a [REDACTED] needle. The needle is designed to facilitate the passage of the mesh assembly through bodily tissues for placement through the obturator foramen.

### 6. Objectives

The primary objective is to evaluate clinical effectiveness of the single incision sling.

### 7. Endpoints

#### Primary Endpoint

The primary endpoint of the study is an assessment of improvement in stress urinary incontinence at 36 months as compared to Baseline by a composite of objective and subject measures: negative cough stress test with protocol required bladder fill procedure (see manual of operations) and a subject self-reported improvement in their condition through the Patient Global Impression of Improvement (PGI-I).

[REDACTED]

## 8. Design

This study is a prospective, non-randomized, parallel cohort, multi-center study.

The final primary endpoint will be assessed once all subjects have completed the 36 month study visit. All subjects will be followed to month 36 or until study completion if discontinued prior to month 36. All study procedures will be standardized for uniformity.

[REDACTED]

[figure not shown]
### 8.1. Scale and Duration

The study will be conducted at up to 30 sites at a rate of approximately 4 subjects per site per month.

[REDACTED]

Once enrolled into the study, subjects will be followed to 36 months post-surgery to be evaluated for the primary endpoint analysis. The total duration of each subject's participation in the study is 36 months from study procedure.

Subjects who undergo a medical intervention (surgical or non-surgical) to treat recurrence, persistence of SUI, or a mesh complication will be followed to 36 months, post the initial study procedure.

## 8.2. Treatment Assignment

This post-approval study is a non-randomized, prospective, parallel cohort study across multiple centers. Subjects will be screened against the study Inclusion/Exclusion criteria and if eligible, enrolled into the study after providing Informed Consent. Approximately 140 subjects will receive the Solyx Sling System as the treatment group, and 140 subjects will receive the Obtryx II Sling System as the control group across the entire study.

To reduce selection bias in this non-randomized study, each study center will be permitted to enroll subjects in only one of the treatment groups. Physicians will be selected based on device and clinical research experience and will decide which device to implant in subjects prior to study initiation at their center. This decision will be documented. All subjects meeting the eligibility criteria at the study center will be screened and enrolled, as applicable.

. Furthermore, at study completion and final data analysis, a comparison of baseline characteristics of patients in the two groups will occur and, if necessary, statistical adjustments performed to control for baseline differences.

Should one study-wide arm reach 140 subjects prior to the other, enrollment will be capped in that arm and the other study arm will remain open to enrollment until it also reaches 140 subjects. Those study centers enrolling the device arm that have met enrollment capacity will be closed, per Sponsor discretion.

### 8.2.1. Treatment and Control

The treatment device in this study is the Solyx Single Incision Sling System and the control device in this study is the Obtryx II Sling System. Please refer to the Directions for Use document for device-specific information.

## 9. Subject Selection

### 9.1. Study Population and Eligibility

This study will enroll adult English-speaking women, who are not pregnant or planning future pregnancies, have been diagnosed with predominant stress urinary incontinence and

who will undergo the surgical placement of a sling as treatment, who may or may not also undergo a concomitant procedure (such as pelvic floor prolapse repair).

To assess for eligibility for this study, inclusion and exclusion criteria are included in Sections 9.2 and 9.3 below.

### **9.2. Inclusion Criteria**

Subjects who meet all of the following criteria may be given consideration for inclusion in this clinical investigation, provided no exclusion criterion (see Section 9.3) is met.

1. Female  $\geq 18$  years of age
2. Willing and able to comply with the study procedures and provide written informed consent to participate in the study (subject or legal representative)
3. Diagnosed with predominant SUI confirmed by positive cough stress test during the protocol required bladder fill procedure (see manual of operations)
4. Confirmed SUI is greater than urge incontinence with MESA
5. Cystometric capacity  $\geq 300$  cc
6. Post-void residual (PVR) of  $\leq 150$  cc
7. Medically approved for general, regional or monitored anesthesia

### **9.3. Exclusion Criteria**

Subjects who meet any one of the following criteria will be excluded from this clinical study.

1. Subjects who are pregnant, lactating, or planning future pregnancies
2. Subjects with a chief complaint of overactive bladder
3. Subjects with a pattern of recurrent urinary tract infections, defined as  $\geq 2$  culture-proven urinary tract infections during a 6-month period prior to surgery or  $\geq 3$  in a 12-month period
4. Subjects with previous surgical procedures for SUI including bulking, urethral sling, bone anchor, Burch procedure, pubo-vaginal sling, and MMK procedure. Excluding Kelly plication, Botox, anterior repair, or Inter-Stim
5. Subjects with prior pelvic organ prolapse surgery who experienced mesh complications
6. Subjects with previous radiation therapy to the pelvis
7. Subjects with known or suspected hypersensitivity to polypropylene mesh
8. Subjects with any of the following confounding conditions:
  - a. Neurogenic bladder
  - b. Urethral stricture and bladder neck contracture

- c. Bladder stones or tumors
  - d. Urinary tract fistula or diverticula
  - e. Pathology which would compromise implant placement including subjects currently taking anticoagulation therapy
  - f. Pathology that would limit blood supply or infections that would compromise healing including chemotherapy, systemic steroids and systemic immunosuppressants
9. Subjects with diabetes and an A1c  $\geq$  7%
10. Non-English speaking subjects
11. Subjects who have participated in an investigational study (medical device or drug) within 30 days of study entry that may impact analysis of this device or have previously participated in the current study

## 10. Subject Accountability

### 10.1. Point of Enrollment

Subjects will be considered enrolled once they have been determined to be eligible against all inclusion and exclusion criteria and have signed Informed Consent. Subjects will be considered Intent-to-Treat (ITT) once the sling procedure has been initiated (i.e. anesthesia administered). All enrolled subjects will be assigned to receive either the treatment or control device by the Investigator prior to the site initiation as sites will be device-specific centers. All ITT subjects who receive the assigned device and have no major protocol deviations will be considered part of the Per Protocol analysis.

### 10.2. Withdrawal

All subjects enrolled in the clinical study (including those withdrawn from the clinical study or lost to follow-up) will be accounted for and documented. If a subject withdraws from the clinical investigation, the reason(s) will be recorded.

Reasons for study withdrawal may include, withdrawn consent, lost to follow-up, subject death or other reasons to be documented on the Case Report Form.

Once a subject withdraws from the study, the Case Report Form will be completed as appropriate up to the point of withdrawal and all Adverse Events shall be closed or documented as appropriate. Withdrawn subjects will be included in the ITT analysis and will not be replaced.

[Redacted]

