##### 12.1.1.2. Sample Size

Statistical power calculation is based on a non-inferiority assumption with a binary outcome.

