##### 12.1.1.3. Statistical Methods

Non-inferiority will be evaluated using a two-sided 90% confidence interval for the treatment difference (single-incision minus transobturator). If the entire confidence interval is above -15%, non-inferiority will be demonstrated. The confidence interval will be calculated based on the pooling of treatment differences across propensity score strata for a binary endpoint, as described in Section 12.3.

[REDACTED]

[REDACTED]

[REDACTED]

[REDACTED]

[REDACTED]

[REDACTED]

[REDACTED]

[REDACTED]

[REDACTED]

[REDACTED]

[REDACTED]

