## 12.2. General Statistical Methods

### 12.2.1. Analysis Sets

The Intent-to-Treat (ITT) subject population includes all subjects who provide written informed consent to be enrolled into the study, met all eligibility criteria, and have a surgery initiated (i.e. anesthesia administered).

The Treated Population includes all subjects who undergo the study surgical procedure. The subject is defined to have successfully completed the surgical procedure (i.e. sling placement successful) and discharged.

The Per Protocol (PP) population includes all subjects in the ITT Population who received the assigned treatment and had no major protocol deviations. All primary [REDACTED] analyses will be performed on both the ITT and per-protocol populations, with ITT considered the main analysis and per protocol as a sensitivity analysis. The analyses will include only the available cases, unless specified otherwise.

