3 ENDPOINT ANALYSIS

3.1 Primary Endpoint

The primary endpoint of the study is treatment success at 36 months defined as a negative cough stress test and a subject-reported improvement in their condition through the Patient Global Impression of Improvement (PGI-I). Improvement per the PGI-I is defined as a response of “A little better”, “Much better”, or “Very much better”. A negative cough stress test is defined as an answer of “No” to the item “Direct observation of urine loss with cough provocation”.

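### Withdrawn women belong to the ITT analysis under Protocol 10.2, but the available-case rule removes them from the Month 36 primary comparison, and no legible text gives them an outcome

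*Protocol*

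**What the plan says.** Protocol 10.2 lists withdrawn consent, loss to follow-up and death among the reasons for withdrawal. It has the case report form completed up to that point and then states: "Withdrawn subjects will be included in the ITT analysis and will not be replaced".

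Protocol 12.2.1 makes ITT the main analysis and per protocol the sensitivity analysis. It then says: "The analyses will include only the available cases, unless specified otherwise". SAP 4.6 repeats that sentence, and redacted text follows in the same section.

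SAP 3.1 defines the primary endpoint as "treatment success at 36 months defined as a negative cough stress test and a subject-reported improvement in their condition", the latter measured by the PGI-I. The legible definition has no term for withdrawal or repeat surgery. Protocol 11.6 does have one: repeat surgery for returning or continuing SUI counts as treatment failure, and those women stay in follow-up to Month 36.

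The Protocol Synopsis gives the expected loss: "Assuming 20% lost to follow-up at 36 months, approximately 280 subjects (140 in each study arm) are planned". The decision rule in Protocol 12.1.1.3 uses a two-sided 90% interval: "If the entire confidence interval is above -15%, non-inferiority will be demonstrated". Protocol Section 8 adds: "All subjects will be followed to month 36 or until study completion if discontinued prior to month 36".

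**The concern.** A woman who withdraws at Month 18 has no Month 36 cough test and no Month 36 PGI-I. Section 10.2 puts her in the ITT analysis, the available-case sentence takes her out of it, and nothing legible assigns her an outcome. Two analysts could follow different sentences and report different primary results.

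The gap is clearest for a woman whose SUI was recorded at an earlier visit, who had no repeat surgery and who then left. Recurrent incontinence is a listed reportable event in Protocol Table 21.4-1, so the record can show that her sling was failing. Section 11.6 does not reach her because she had no surgery.

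In a non-inferiority comparison the direction matters. If women with failed slings leave more often, both observed success rates rise. The rate in the worse arm rises more because that arm has more failures to lose. The difference moves toward zero, which favours a non-inferiority conclusion, and this needs no difference between arms in the dropout mechanism.

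**Working it through.** **Inputs from the documents.** 140 women per arm and 20% loss (Protocol Synopsis); margin 15 points and two-sided 90% interval, so one-sided 5% (Protocol 12.1.1.3). The assumed success rates and power are not legible in Protocol 12.1.1.2, so the success rates below are assumptions. Intervals are unstratified Wald intervals, whereas the plan pools across propensity strata.

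**The plan's own figure.** 112 / (1 − 0.20) = 140, so 140 per arm corresponds to 112 evaluable. Expected missing: 0.20 × 140 = 28 per arm, 56 of 280 in all. The full sample size derivation cannot be checked.

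**Error rate when failures leave more often, same mechanism in both arms.** Take a true null of 85% (Obtryx II) and 70% (Solyx). Let f be the probability that a failure is lost and s the probability that a success is lost, both common to the two arms. The average failure proportion is (0.15 + 0.30)/2 = 0.225, so 20% average loss requires

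0.225 f + 0.775 s = 0.20.

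The observed success rate in an arm with true rate p is p(1 − s) / [p(1 − s) + (1 − p)(1 − f)]. The chance of declaring non-inferiority is Φ((d + 0.15)/SE − 1.645), where d is the observed difference and SE uses the expected numbers retained.

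- f = 0.20: s = 0.20, d = −15.0 points, error 5%. Loss unrelated to outcome does no harm.
- f = 0.30: s = (0.20 − 0.0675)/0.775 = 0.171. Obtryx II: 0.7047/(0.7047 + 0.1050) = 87.0%. Solyx: 0.5803/(0.5803 + 0.2100) = 73.4%. d = −13.6 points, SE = 0.0525, error Φ(0.266 − 1.645) = 8.4%.
- f = 0.40: s = (0.20 − 0.0900)/0.775 = 0.142. Obtryx II: 0.7294/(0.7294 + 0.0900) = 89.0%. Solyx: 0.6006/(0.6006 + 0.1800) = 76.9%. d = −12.1 points, SE = 0.0498, error Φ(0.588 − 1.645) = 14.5%.
- f = 0.40 with Obtryx II at 80% or 90% and Solyx 15 points lower: 12.6% and 17.3%.

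**How far a passing result depends on the missing women.** Assume equal observed rates of 80%, 85% or 90% among 112 per arm. The available-case lower limits are −8.7%, −7.9% and −6.5%, so all pass.

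- Equal 20% loss, all missing counted as failures: −9.4%, −9.2%, −8.8%. The limit moves by 0.7 to 2.3 points and the conclusion holds.
- Loss of 25% in Solyx and 15% in Obtryx II: available cases give −8.7%, −8.0%, −7.1% and pass; missing as failure gives −17.3%, −17.7%, −18.1% and fails.
- Tipping point, 28 missing per arm, missing Obtryx II women succeeding at the observed rate: non-inferiority holds only if at least 13, 14 and 14 of the 28 missing Solyx women are successes. At 85%, for example, Solyx is (95 + 14)/140 = 77.9% and Obtryx II is (95 + 24)/140 = 85.0%, with lower limit −14.8%.

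**The case against.** The strongest reply is that the two rules can coexist. Being included in the ITT analysis may mean only that withdrawn women stay in the analysis set and contribute what was collected before they left. SAP 4.6 censors time-to-event analyses at the end of participation, so they do contribute there. The available-case sentence allows exceptions, and the places where one would sit, in SAP 4.6 and after SAP 3.1.3, are redacted. This stands as a limit on the point: it cannot be said that the plan has no imputation or missing-data sensitivity analysis. It does not supply a Month 36 outcome in the legible text.

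A reader might go further and infer that the plan discards known failures in general. Section 11.6 does not support that. It already classes repeat surgery for SUI as failure and keeps those women in follow-up, which may be one of the permitted exceptions. What is unsettled is whether the rule governs the SAP endpoint, and whether it still applies to a woman who later withdraws.

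A reader might also take Section 8 as a competing third rule, under which discontinued women are followed to study completion. The wording is loose and may mean only the subject's own exit, so it calls for clarification.

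On size, fixing loss at exactly 20% in each arm gives higher error rates, 9.9% at f = 0.30 and 18.8% at f = 0.40. That set-up loses successes at different rates by arm (at f = 0.40, 11.4% in Solyx and 16.5% in Obtryx II), so it does not describe a common mechanism.

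Finally, equal loss with no true difference between devices barely moves the interval. That is correct, but it does not address the error rate when Solyx is truly 15 points worse.

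**Conclusion.** The point holds. On the legible text, Protocol 10.2 and the available-case rule do not fit together for a binary endpoint measured only at Month 36, and the main ITT analysis of that endpoint becomes an analysis of women with Month 36 data. The expected 28 missing per arm are enough to matter. Under a common mechanism in which failures leave more often, the one-sided error is about 8% to 15% instead of 5%, or 13% to 17% at the heavier loss across control rates of 80% to 90%.

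These sizes rest on assumed success rates, assumed loss rates among failures and an unstratified interval; the documents give no evidence on how loss relates to outcome. The direction of the bias is firmer than its amount. The documents do not support a claim that imputation is absent.

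**What to change.** 1. Carry the Section 11.6 rule into SAP 3.1, so that a woman with repeat surgery for SUI is a failure even if she later withdraws.
2. Make the main ITT analysis include every ITT woman. Multiply impute the remaining missing Month 36 outcomes by arm and propensity stratum, using earlier-visit cough test and PGI-I results and the recorded reason for withdrawal. Then compute the stratum-pooled difference and 90% interval on the imputed data. The assessment schedule is redacted, so confirm which earlier visits collect these measures.
3. Keep the available-case analysis as a sensitivity analysis. Add a missing-as-failure or tipping-point analysis, because the imputation assumes data missing at random and cannot capture failures that arise after the last visit.
4. Clarify the Section 8 sentence so that it agrees with 10.2.
5. If the redacted SAP text already has imputation as a sensitivity analysis, exchange its role with that of the available-case analysis.

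The cost is protocol and SAP wording, modest programming, reliance on an imputation model and slightly lower reported success rates. The design, the sample size and the care of subjects do not change.
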